7.3.2 Timing of Dose Administration

Trial treatment should be administered on Day 1 of each cycle after all procedures/assessments have been completed as detailed on the Trial Flow Chart (section 6.0).

- Pembrolizumab 200 mg will be administered on an outpatient basis as a 30 minute IV infusion every 3 weeks. Sites should make every effort to target infusion timing to be as close to 30 minutes as possible. However, given the variability of infusion pumps from site to site, a window of -5 minutes and +10 minutes is permitted (i.e., infusion time is 30 minutes: -5 min/+10 min).
- Pembrolizumab may be administered up to 3 days before or after the scheduled Day 1 of each cycle due to administrative reasons.

7.3.2 Dose Modification and toxicity management for immune-related AEs associated with pembrolizumab

AEs associated with pembrolizumab exposure may represent an immunologic etiology. These immune-related AEs (irAEs) may occur shortly after the first dose or several months after the last dose of pembrolizumab treatment and may affect more than one body system simultaneously. Therefore, early recognition and initiation of treatment is critical to reduce complications.

- Based on existing clinical study data, most irAEs are reversible and could be managed with interruptions of pembrolizumab, administration of corticosteroids and/or other supportive care.
- For suspected irAEs, ensure adequate evaluation to confirm etiology or exclude other causes. Additional procedures or tests such as bronchoscopy, endoscopy, skin biopsy may be included as part of the evaluation. Based on the severity of irAEs, withhold or permanently discontinue pembrolizumab and administer corticosteroids.
- Dose modification and toxicity management guidelines for irAEs associated with pembrolizumab are provided in Table 7.3.2.

Table 7.3.2 Dose modification and toxicity management guidelines for immune-related AEs associated with pembrolizumab

General instructions:				

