9.1.7.4.1 Safety Follow-Up TRIAL Phase Visit

The mandatory Safety Follow-Up Visit should be conducted approximately 30 days after the last dose of study treatment or before the initiation of a new anti-cancer treatment, whichever comes first. All AEs that occur prior to the Safety Follow-Up Visit should be recorded. Participants with an AE of Grade > 1 will be followed until the resolution of the AE to Grade 0-1 or until the beginning of a new anti-cancer therapy, whichever occurs first. SAEs that occur within 90 days of the end of treatment or before initiation of a new anti-cancer treatment should also be followed and recorded. Participants who are eligible for retreatment with pembrolizumab (as described in 7.3.5) may have up to two safety follow-up visits, one after the Initial Treatment Period and one after the Second Course Treatment.

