9.2.1 Definitions for Adverse Event and Serious Adverse Event

An Adverse Event (AE) is defined as any untoward medical occurrence in a patient or clinical investigation participant administered a medicinal product and which does not necessarily have to have a causal relationship with this treatment. An AE can therefore be any unfavourable and unintended sign (including an abnormal laboratory finding, for example), symptom, or disease temporally associated with the use of a medicinal product or protocol-specified procedure, whether or not considered related to the medicinal product or protocol-specified procedure. Any worsening (i.e., any clinically significant adverse change in frequency and/or intensity) of a pre-existing condition that is temporally associated with the use of the investigational products, is also an AE.

AEs may occur during the course of the use of investigational product in clinical trials, or as prescribed in clinical practice, from overdose (whether accidental or intentional), from abuse and from withdrawal.

A Serious Adverse Event (SAE) is any adverse event that:

- Results in death;
- Is life threatening;
- Results in persistent or significant disability/incapacity;

- Results in or prolongs an existing inpatient hospitalization;
- Is a congenital anomaly/birth defect;
- Is another important medical event
- **Note:** In addition to the above criteria, adverse events meeting either of the below criteria, although not serious per ICH definition, are reportable to the delegated pharmacovigilance service and to Merck Global Safety (if concerning pembrolizumab, Attn: Worldwide Product Safety; [contact]) in the same timeframe as SAEs to meet certain local requirements. Therefore, these events are considered serious by Merck for collection purposes.
- Is a new cancer (that is not a condition of the study);
- Is associated with an overdose.

Refer to Table 9.2 for additional details regarding each of the above criteria.

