9.2.2 Reporting of Adverse Events

AEs will be collected from the time the first dose of study medication (either pembrolizumab or temozolomide) is administered until 30 days following discontinuation of study treatment. SAEs will be collected over the same time period as stated above for AEs of temozolomide, or up to 90 days for pembrolizumab. In addition, any SAE assessed as related to study participation, study medication or concomitant medication must be recorded from the time a subject consents to participate in the study up to and including any follow-up contact. After discontinuation of study medication, the investigator will monitor all AEs/SAEs that are ongoing until resolution or stabilization of the event or until the subject is lost to follow-up.

Reporting criteria for AEs/SAEs:

- All AEs, SAEs and other reportable safety events that occur after the consent form is signed but before planned treatment initiation must be reported by the investigator if the event cause the participant to be excluded from the study.
- All AEs must be reported by the investigator from the time of treatment allocation through 30 days following cessation of study treatment.
- SAEs regarding pembrolizumab must be reported by the investigator from the time of treatment allocation through 90 days (pembrolizumab) or 30 days (temozolomide) following cessation of study treatment, or 30 days following cessation of study treatment if the participant initiates new anticancer therapy, whichever is earlier.
- All pregnancies must be reported by the investigator from the time of treatment allocation through 120 days (pembrolizumab) or 90 days (temozolomide) following cessation of study treatment, or 30 days following cessation of study treatment if the participant initiates new anticancer therapy, whichever is earlier.

- Any SAE brought to the attention of an investigator at any time outside of the time period specified above must be reported immediately by the investigator if the event is considered to be study drug-related.
- A death on study requires reporting regardless of causality and attribution to treatment or other cause must be provided. Death due to disease progression is not to be reported as an AE. Deaths that occur beyond 30 days after the end of study drug administration/initiation of an alternate therapy, do not qualify as SAEs.

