9.2.3 Reporting of Serious Adverse Events

Each adverse event is to be classified by the investigator as SERIOUS or NON-SERIOUS. This classification of the seriousness of the event determines the reporting procedures to be followed.

In order to comply with SAEs reporting responsibilities, the Sponsor of the study will appoint a delegated CRO as "Third Party Pharmacovigilance Provider". If a SAE occurs, the Pharmacovigilance has to be notified by fax or by e-mail, using the designated form, within 24 hours of awareness of the event by the Investigator.

Moreover, in case of any SAE, or follow up to a SAE, including death due to any cause whether or not related to the Merck product (pembrolizumab), it must be reported also to Merck Global Safety within 2 working days. Additionally, any SAE considered by the investigator to be related to pembrolizumab, which is brought to the attention of the investigator either at any time between informed consent to the end of the specified safety follow-up period, or at any time outside of the follow-up time period, must also be reported immediately to Merck Global Safety (Attn: Worldwide Product Safety; [contact]).

Investigators are not obligated to actively seek AE or SAE or other reportable safety events in former study participants. However, if the investigator learns of any SAE, including a death, at any time after a participant has been discharged from the study, and he/she considers the event to be reasonably related to the study treatment or study participation, the investigator must promptly notify Merck Global Safety (Attn: Worldwide Product Safety; [contact]).

The initial report should be followed by submission of more detailed adverse event information within 5 calendar days after the Investigator first became aware of the serious adverse event. Reporting requirements for adverse events are summarized in the table below.

Gravity	Reporting Time	Type of Report
---------	----------------	----------------

SERIOUS	Within 24 hours from awareness by the investigator	Initial report on SAE report form + case report form
	Within 5 calendar days from initial report	Follow-up/Final report on SAE report form
NON SERIOUS	Per case report form submission procedure	Case report form

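### Section 9.2.2 denies SAE status to deaths after day 30, which contradicts the protocol's own 90-day pembrolizumab SAE window and could leave some late deaths unclassified

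*Combined protocol and SAP*

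**What the plan says.** Section 9.2.2 sets the collection period first: "SAEs will be collected over the same time period as stated above for AEs of temozolomide, or up to 90 days for pembrolizumab". Ordinary AEs are collected for 30 days after treatment. The reporting list in the same section repeats the SAE periods, "through 90 days (pembrolizumab) or 30 days (temozolomide) following cessation of study treatment", and shortens them in one case: "or 30 days following cessation of study treatment if the participant initiates new anticancer therapy, whichever is earlier". Section 9.1.7.4.1 also refers to "SAEs that occur within 90 days of the end of treatment", with its own limit at the start of a new anticancer treatment.

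Section 9.2.1 lists "Results in death" as a criterion that makes an adverse event serious, with no time limit. Section 9.2.3 requires SAEs to go to the drug supplier's safety unit, "including death due to any cause whether or not related to the Merck product (pembrolizumab").

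The last bullet of the list in 9.2.2 deals with deaths. It requires a death on study to be reported with an attribution whatever the cause, and it exempts deaths from disease progression from AE reporting. It then ends: "Deaths that occur beyond 30 days after the end of study drug administration/initiation of an alternate therapy, do not qualify as SAEs". That sentence makes no distinction between the two drugs.

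**The concern.** The closing sentence takes away SAE status according to outcome. Of two serious events at the same time after pembrolizumab, the non-fatal one counts and the fatal one does not.

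The safety of pembrolizumab, both after temozolomide priming and in cohort D, is a stated secondary objective (section 5.2). The protocol expects late toxicity: the section 7.3.2 on immune-related events says that they "may occur shortly after the first dose or several months after the last dose of pembrolizumab treatment". The 90-day window covers part of that period.

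SAE status also decides what happens next. Under 9.2.3 the 24-hour notification applies to serious events, and pharmacovigilance looks for SUSARs among the SAEs that investigators report. A death that a site does not class as an SAE may reach neither step.

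**Working it through.** There is no stated figure to reproduce. The check sets the rules side by side and then does some short arithmetic.

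**Step 1: length of the conflict.** The pembrolizumab SAE window is 90 days (9.2.2, 9.1.7.4.1) and the cut-off for deaths is 30 days (9.2.2, last sentence of the list). The difference is 90 − 30 = 60 days, that is days 31 to 90, and 60/90 = 67% of the window. This is a share of calendar time, not of deaths or patients. For temozolomide the difference is 30 − 30 = 0 days.

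**Step 2: which deaths are affected.** Take a death on day 60 after the last dose.

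| Situation | SAE windows and definition | Last sentence of the list | Conflict over the window |
|---|---|---|---|
| Pembrolizumab; no new therapy; not progression; judged unrelated | SAE | Not an SAE | Yes, clear |
| Same, but judged drug-related | SAE, and reportable at any time | Not an SAE | Yes; the label is ambiguous |
| Death due to progression | Not an AE | Not an SAE | None |
| New anticancer therapy started | Window is 30 days after cessation | Not an SAE, if the clock runs from the end of study drug | None |
| Temozolomide only | Window is 30 days | Not an SAE | None |

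**Step 3: can a death in the first row be picked up elsewhere?** Ordinary AE collection stops at 30 days, so a fatal event that first arises on days 31 to 90 has no AE route to fall back on. The rule on late drug-related events, and the related-event rules in 9.2.3, start from an SAE that the investigator considers related. An unrelated death does not meet them. For a related death it is unclear whether they apply once the death has been said not to qualify.

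**Step 4: the start of the clock.** The slash in the closing sentence allows 30 days to run from the end of study drug or from the start of an alternate therapy. Suppose a new therapy starts on day 10. On the second reading the cut-off is day 10 + 30 = day 40. The SAE bullet in 9.2.2 closes at day 30, and 9.1.7.4.1 can be read as closing at day 10.

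**Step 5: illustrative size.** The planned numbers are 20 in cohort P, up to 34 in cohort D and 54 in the TRIAL Phase (sections 10.2 and 2.0). One unclassified death lowers the fatal SAE proportion by 1/20 = 5.0 points, 1/34 = 2.9 points or 1/54 = 1.9 points. Exact (Clopper-Pearson) 95% limits for cohort P are:

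- 1/20: the lower limit is 1 − 0.975^(1/20) = 0.1%. The upper limit solves (1 − p)^20 + 20p(1 − p)^19 = 0.025, which gives p = 24.9%.
- 0/20: the lower limit is 0. The upper limit is 1 − 0.025^(1/20) = 16.8%.

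**The case against.** A reader might infer that late fatal events would disappear from the safety result. The documents do not support that, for these reasons:

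- The same bullet in 9.2.2 requires deaths on study to be reported and attributed, whatever the cause.
- Related SAEs are recorded up to any follow-up contact and stay reportable outside the window. Under 9.2.3, related deaths that come to light after discharge must also be notified.
- Seriousness belongs to the adverse event. An event that was life-threatening or led to hospitalization is serious on that ground, even if the later death is not counted.
- Survival follow-up (9.1.7.4.3) runs until death, so the deaths enter the overall survival data.
- No fatal SAE rate is defined as an endpoint. Section 10.3.3 says only that adverse events are reported as proportions, without a time window.

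All of this stands, and it limits the point to classification. It does not close the gap. The rule on deaths on study names no deadline, form or recipient, and does not say what on study means. Survival follow-up is a telephone check every 12 weeks that serves overall survival, not the attribution of toxicity. The routes for related events depend on the investigator's own judgement of relatedness and on the SAE label that the closing sentence removes.

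**Conclusion.** The closing sentence on deaths in 9.2.2 is wrong as written. It contradicts the 90-day pembrolizumab window in 9.2.2 and 9.1.7.4.1, the SAE definition in 9.2.1 and the reporting of death from any cause in 9.2.3.

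The contradiction is certain, because it can be read off the text. The consequence is a possibility: deaths in the clear gap could go unclassified as SAEs, and drug-related deaths on days 31 to 90 have an uncertain status. Any resulting error in the fatal SAE count goes one way, downwards.

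Its size is unknown. The cohort P illustration assumes 20 treated patients and exactly one such death, and nothing in the documents says how many to expect. The primary endpoint, the error rates and the sample size are untouched. This should be corrected, but it does not put the trial's main result in doubt.

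**What to change.** Delete the closing sentence, or reword it so that deaths follow the SAE windows that 9.2.2 already gives: 90 days after pembrolizumab, 30 days after temozolomide, and 30 days after cessation of study treatment when new anticancer therapy starts. Keep the exception for deaths due to disease progression.

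If any 30-day limit remains, state the one date from which it is counted. In the same amendment, bring 9.1.7.4.1, 9.2.1, 9.2.2 and 9.2.3 into agreement, including the different ways in which 9.1.7.4.1 and 9.2.2 treat the start of new therapy.

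The cost is a short text amendment and a note to sites. No new data collection is needed, since SAEs are already to be collected for 90 days after pembrolizumab.

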9.2.3 Reporting of Serious Adverse Events

Each adverse event is to be classified by the investigator as SERIOUS or NON-SERIOUS. This classification of the seriousness of the event determines the reporting procedures to be followed.

In order to comply with SAEs reporting responsibilities, the Sponsor of the study will appoint a delegated CRO as "Third Party Pharmacovigilance Provider". If a SAE occurs, the Pharmacovigilance has to be notified by fax or by e-mail, using the designated form, within 24 hours of awareness of the event by the Investigator.

Moreover, in case of any SAE, or follow up to a SAE, including death due to any cause whether or not related to the Merck product (pembrolizumab), it must be reported also to Merck Global Safety within 2 working days. Additionally, any SAE considered by the investigator to be related to pembrolizumab, which is brought to the attention of the investigator either at any time between informed consent to the end of the specified safety follow-up period, or at any time outside of the follow-up time period, must also be reported immediately to Merck Global Safety (Attn: Worldwide Product Safety; [contact]).

Investigators are not obligated to actively seek AE or SAE or other reportable safety events in former study participants. However, if the investigator learns of any SAE, including a death, at any time after a participant has been discharged from the study, and he/she considers the event to be reasonably related to the study treatment or study participation, the investigator must promptly notify Merck Global Safety (Attn: Worldwide Product Safety; [contact]).

The initial report should be followed by submission of more detailed adverse event information within 5 calendar days after the Investigator first became aware of the serious adverse event. Reporting requirements for adverse events are summarized in the table below.

Gravity	Reporting Time	Type of Report
---------	----------------	----------------

SERIOUS	Within 24 hours from awareness by the investigator	Initial report on SAE report form + case report form
	Within 5 calendar days from initial report	Follow-up/Final report on SAE report form
NON SERIOUS	Per case report form submission procedure	Case report form

If for any reason the SAE form transmission is not possible, Pharmacovigilance should be informed by phone of the occurrence of the event. In this exceptional case, Pharmacovigilance will complete a SAE form with information received, which will be sent to the investigator for confirmation, and in the meanwhile Pharmacovigilance procedures will be initiated.

SAEs should also be reported on the AE case report form (CRF). The form to be used for SAE expedited reporting is not the same as the AE CRF, but where the same data are collected, the forms must be completed in a consistent manner. For example, the same AE term should be used on both forms.

Pharmacovigilance assesses each SAE reported by the study Investigators to identify any suspected unexpected serious adverse reactions (SUSAR), i.e. serious adverse events considered at least possible associated to the study treatment by the Investigator and not listed in the IMP reference document(s) and provide this information to the sponsor for the final evaluation. If a SAE is assessed as a possible SUSAR, the sponsor, through delegated Pharmacovigilance, may urgently require further information to the Investigator. Pharmacovigilance will issue a SUSAR notification whenever appropriate, and submit it to all concerned recipients according to current law and following sponsor's indication.

Follow-up information is to be reported on a new SAE form and transmitted to the same fax number as the initial report. A follow-up report is to be filled in, not only to complete the information provided on the initial report but also to modify any incorrect data. The SAE fax delivery confirmation sheets must be retained at the study sites.

At the end of the study all original SAE report forms are to be collected in the Investigator File, while the corresponding copies must be retained by the CRO personnel and archived in the TMF.

For the expectedness assessment of each case with pembrolizumab, the Sponsor will use the Investigator Brochure as the Reference Safety Information. For the expectedness assessment of each case with temozolomide, the Sponsor will use the SmPC (Undesirable Effects, section 4.8) and the safety data of the studies published in colorectal cancer (Amatu et al., 2013, 2016).

9.2.4 Definition and Reporting of an Overdose for This Protocol

Temozolomide

Doses of 500, 750, 1,000, and 1,250 mg/m² (total dose per cycle over 5 days) have been evaluated clinically in patients. Dose-limiting toxicity was haematological and was reported with any dose but is expected to be more severe at higher doses. An overdose of 10,000 mg (total dose in a single cycle, over 5 days) was taken by one patient and the adverse reactions

reported were pancytopenia, pyrexia, multiorgan failure and death. There are reports of patients who have taken the recommended dose for more than 5 days of treatment (up to 64 days) with adverse events reported including bone marrow suppression, with or without infection, in some cases severe and prolonged and resulting in death. In the event of an overdose, haematological evaluation is needed. Supportive measures should be provided as necessary.

Pembrolizumab

For purposes of this study, an overdose of pembrolizumab will be defined as any dose of 1,000 mg or greater (≥ 5 times the indicated dose). No specific information is available on the treatment of overdose of pembrolizumab. In the event of overdose, the participant should be observed closely for signs of toxicity. Appropriate supportive treatment should be provided if clinically indicated.

If an adverse event(s) is associated with (“results from”) the overdose of a Merck product, the adverse event(s) is reported as a serious adverse event, even if no other seriousness criteria are met.

If a dose of Merck’s product meeting the protocol definition of overdose is taken without any associated clinical symptoms or abnormal laboratory results, the overdose is reported as a non-serious Event of Clinical Interest (ECI), using the terminology “accidental or intentional overdose without adverse effect.”

All reports of overdose with and without an adverse event must be reported within 24 hours to Pharmacovigilance and within 2 working days hours to Merck Global Safety (Attn: Worldwide Product Safety; [contact]).

